It provides information about procedures for entering participants into the trial, and provides sufficient detail to enable: an understanding of the background, rationale, objectives, trial population, intervention, methods, statistical analyses, ethical considerations, dissemination plans and administration of the trial; replication of key aspects of trial methods and conduct; and appraisal of the trial's scientific and ethical rigour from the time of ethics approval through to dissemination of the results. The protocol should not be used as an aide-memoire or guide for the treatment of other patients. Every care has been taken in drafting this protocol, but corrections or amendments may be necessary. These will be circulated to registered investigators in the trial.

MeiraGTx UK II Ltd. supports the commitment that its trials adhere to the SPIRIT guidelines. As such, the protocol template is based on an adaptation of the Standard Protocol Items: Recommendations for Interventional Trials (SPIRIT) 2012 Statement for protocols of clinical trials (Chan *et Al.* 2013¹). The SPIRIT Statement Explanation and Elaboration document (Chan *et Al.* 2013²) can be referred to, or a member of MeiraGTx UK II Ltd. Clinical Operations team can be contacted for further detail about specific items.

1.1 Compliance

The trial will be conducted in compliance with the approved protocol and all applicable regulations. UK sites will comply with the principles of Good Clinical Practice (GCP) as laid down by the Commission Directive 2005/28/EC with implementation in national legislation in the UK by Statutory Instrument 2006/1928 and subsequent amendments, Advanced Therapy Medicinal Products (ATMP) Regulations (EC) No 1394/2007, the Human Tissue (Quality and Safety for Human Application) Regulations 2007, and the UK Data Protection Act. US sites will comply with 21 CFR 312 in the Code of Federal Regulations, and the NIH Guidelines for Research Involving Recombinant or Synthetic Nucleic Acid Molecules (November 2013).

The participating sites will inform MeiraGTx UK II Ltd. as soon as they are aware of a possible serious breach of compliance, so that MeiraGTx UK II Ltd. can fulfil its requirement to report the breach if

necessary, within the relevant applicable timelines specified in each country in which the study is being conducted. For the purposes of reporting, a 'serious breach' is one that is likely to affect to a significant degree:

- The safety or physical or mental integrity of the participants in the trial, or
- The scientific value of the trial.

1.3 Structured trial summary

Primary Registry and Trial Identifying	EudraCT 2016-003967-21
Number	
Secondary Identifying Numbers	MeiraGTx UK II Ltd. registration number: MGT009
Sponsor	MeiraGTx UK II Ltd.
Contact for Public Queries	[contact]
Contact for Scientific Queries	
Public Title	RPGR XLRP trial
Scientific Title	An open label, multi-centre, Phase I/II dose escalation trial of a
	recombinant adeno-associated virus vector AAV2/5-
	hRKp.RPGR for gene therapy of adults and children with X-
	linked Retinitis Pigmentosa owing to defects in RPGR
Countries of Recruitment	United Kingdom, United States of America
Health Condition(s) or Problem(s)	X-linked Retinitis Pigmentosa
Studied Intervention(s)	Onen label, description
intervention(s)	Open label, dose-escalation
Key Inclusion and Exclusion Criteria	Key Inclusion Criteria:
,,	Males aged 5 years or older (children will be included only)
	once the maximal tolerated dose has been determined)
	With Retinitis Pigmentosa caused by mutations in RPGR
	Evidence of relative preservation of retinal structure at the
	macula
	Able to undertake age-appropriate clinical assessments
	Willing to give consent for the use of blood and blood
	components collected throughout the trial for the
	investigation of immune response to ATIMP
	Key Exclusion Criteria:
	Intra-ocular surgery within 3 months of screening
	Ocular or systemic disorder that may preclude subretinal
	surgery and/or interfere with interpretation of the study
	results.
	Participated in another research study involving an
	investigational therapy for ocular disease within the last 6
	months

 Have any other condition that the Principal Investigator (PI) considers makes them inappropriate for entry into the trial Are unwilling to consider the possibility of entry into a
subsequent longer term follow up study Phase I/II, open-label, multi-centre, dose escalation in adults, followed by dose confirmation in children, followed by further randomised dose confirmation against a control arm in adults and children with XLRP owing to defects in RPGR
Q3 2017
Up to 71 participants
The primary outcome is safety of subretinal administration of AAV2/5-hRKp.RPGR. Safety is defined as the absence of ATIMP-related: Reduction in visual acuity by 15 ETDRS letters or more Severe unresponsive inflammation Infective endophthalmitis Ocular malignancy Grade III or above non-ocular SUSAR Safety will be assessed for 12 months after the intervention in this study, and a further 4 years in a separate follow on study (for deferred arm patients' safety will be assessed for 6 months after the intervention in this study and a further 4½ years in a
separate follow on study).
The secondary outcomes are measures of the efficacy of the intervention, which will be performed on an individual participant basis and will be descriptive in nature. Efficacy will be assessed at several time points between 3 to 12 months after the intervention: 1) Slowing or halting of progressive deterioration in retinal structure or visual function that is greater than the baseline variation for that test and is sustained for at least two consecutive assessments. Slowing or halting of progression over time may be facilitated by comparing identical structural and functional assessments acquired prior to intervention/injection to better determine rate of change over time in this slowly progressive disease. 2) Any improvement in visual function from baseline that is greater than the baseline variation for that test and is sustained for at least two consecutive assessments. 3) Any improvement in retinal function from preintervention that is greater than baseline variation and measurable by electrophysiology (pattern ERG, multifocal ERG or full-field ERG). 4) Health- and vision-related quality of life measures (HRQoL, VRQoL).

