4.2 Objectives

4.2.1 Primary Objective

The primary research objective is to assess the safety of the ATIMP, AAV2/5-hRKp.RPGR, for *RGPR-ORF15* gene replacement in the retina of patients with *RPGR* XLRP.

Safety is defined as the absence of an ATIMP-related:

- Reduction in visual acuity by 15 ETDRS letters or more
- Severe unresponsive inflammation (defined below)
- Infective endophthalmitis
- Ocular malignancy
- Grade III or above non-ocular SUSAR (see section 5.11.3)

Severe unresponsive inflammation will be defined according to the Standardisation of Uveitis Nomenclature (SUN) Working Group grading system (Jabs *et Al.* 2005) i.e.

- anterior chamber cells 3+ (26-50 cells in a field size of 1mm x 1-mm slit-beam), or
- anterior chamber flare 3+ (marked, iris and lens details hazy), or
- vitreous haze 3+ (Ophthalmology 1985; 92:467-71)

that fails to improve by 2 steps (or to grade 0) during a 6 week period.

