5.5 Outcomes

5.5.1 Primary Outcomes

The primary safety outcome is defined as absence of any of the below occurring during the 9 weeks following administration, at least possibly related to the ATIMP, not surgery alone:

Reduction in visual acuity by 15 ETDRS letters or more

- Severe unresponsive inflammation
- Infective endophthalmitis
- Ocular malignancy
- Grade III or above non-ocular SUSAR (see section 5.11.3)

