5.10.3.2 Statistical Methods – Outcomes

The primary outcome is safety of subretinal administration of the ATIMP defined as any of the below occurring during the 9 weeks following administration, at least possibly related to the ATIMP, not surgery alone:

- Reduction in visual acuity by 15 ETDRS letters or more
- Severe unresponsive inflammation (defined below)

- Infective endophthalmitis
- Ocular malignancy
- Grade III or above non-ocular SUSAR (see section 5.11.3)

The number of DLEs at each dose level will be summarised by cohort and overall.

Safety data relating to participants at all dose levels will allow estimation of an upper bound for the true event rate through a 95% confidence interval.

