1.3. Statistical Hypotheses for Trial Objectives

1.3.1. Primary Safety Hypothesis

The objective of the dose escalation phase is to estimate the proportion of subjects who experienced the primary safety outcome. No formal hypothesis testing will be conducted.

The primary safety outcome is defined as any of the events delineated below and occurring during the 9 weeks following administration, at least possibly related to the ATIMP, not the surgery alone:

- Reduction in visual acuity by 15 Early Treatment Diabetic Retinopathy Study (ETDRS) letters or more
- Severe unresponsive inflammation (defined in Section 4.2.1 of the protocol)
- Infective endophthalmitis
- Ocular malignancy
- Grade III or above non-ocular suspected unexpected serious adverse reaction (SUSAR) (Protocol MGT009, Section 5.11.3.4.2 Severity or Grading of Adverse Events).

Safety will be assessed for 12 months following ATIMP administration for immediate treatment participants in this study (Protocol MGT009) by study phases (dose escalation, dose confirmation and expansion phases) and overall, comparing with 6 months data in deferred treatment arm prior to treatment. Safety outcome captured in a separate long-term follow-up study (Protocol MGT010) for a further 4 years will be summarized separately.

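### The safety objective has no time limit, but the analysed primary safety outcome stops at 9 weeks, and no table gives the same composite over the in-study follow-up

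*Protocol*

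**What the plan says.** The same five event types appear throughout: a loss of 15 or more ETDRS letters, severe unresponsive inflammation, infective endophthalmitis, ocular malignancy, and a Grade III or higher non-ocular SUSAR. The time limit differs.

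- Protocol 4.2.1 (primary objective): "Safety is defined as the absence of an ATIMP-related" event from the list. No time limit.
- Protocol 1.3 (summary, primary outcome entry): the same definition, no time limit, followed by "Safety will be assessed for 12 months after the intervention in this study" and, for the other arm, "for deferred arm patients' safety will be assessed for 6 months after the intervention in this study".
- Protocol 5.5.1: "The primary safety outcome is defined as absence of any of the below occurring during the 9 weeks following administration".
- Protocol 5.10.3.2: "The primary outcome is safety of subretinal administration of the ATIMP defined as any of the below occurring during the 9 weeks following administration".
- SAP 1.3.1: "The primary safety outcome is defined as any of the events delineated below and occurring during the 9 weeks following administration". The same section then says that safety is assessed over 12 months in immediate-treatment participants.
- SAP Section 6: the proportion with the primary safety outcome and its 95% confidence interval, by phase, treatment group and overall, with deferred participants after treatment tabulated separately. A similar analysis is planned for dose-limiting events (DLEs) in the escalation phase.
- Protocol 4.3.2.1: the DLE has the same five event types and the same 9 weeks.
- SAP 6.1: an adverse event is treatment-emergent only if it occurs within 6 months of administration.

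**The concern.** The objective asks whether these five events occur after the product is given. The analysed outcome asks whether they occur in the first 9 weeks. A participant with an ATIMP-related 15-letter loss at month 6 fails the safety definition in Protocol 4.2.1 but is not counted in the proportion and interval of SAP Section 6.

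The 9 weeks match the DLE window exactly. The amendment log entry for version 3 explains that length for DLEs, as the 8-week steroid course plus one week. In the escalation phase the primary outcome as defined therefore adds nothing to the DLE count. No planned table gives the composite beyond week 9, although the participants are followed and the events recorded.

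At stake is how the headline safety figure will be read. A reader of the summary would take it to describe 12 months.

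**Working it through.** The plan has no figure of its own to reproduce here: Protocol 5.7 gives no formal sample size calculation, and neither document states an expected event rate.

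**1. Calendar time covered** (follow-up from Protocol 1.3; window from Protocol 5.5.1)
- Escalation, paediatric and immediate participants: 9/52 = 17.3% inside, (52 − 9)/52 = 82.7% outside.
- Deferred participants after treatment: 9/26 = 34.6% inside, (26 − 9)/26 = 65.4% outside.

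**2. Scheduled visits covered** (Protocol Tables 3 and 4)
- Immediate-arm schedule: D1, D3, W1, W2, W4, W6, W9, M3, M6, M9, M12. By week 9: 7/11 = 64%.
- Deferred schedule after treatment: D1, D3, W1, W2, W4, W6, W9, M3, M6. By week 9: 7/9 = 78%.
- These counts take the W9 visit as inside the window. Its SAP window runs to Day 72, against a target of Day 64.

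Steps 1 and 2 measure different things, and neither is a share of events.

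**3. Effect on the inflammation component**
The event requires no sufficient improvement over 6 weeks (Protocol 4.2.1). If the whole criterion must be met inside the window, onset must be by about week 9 − 6 = 3. The documents do not say whether onset or completion must fall within the 9 weeks.

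**4. What else would show a late event**
- AEs are recorded to the end of the trial (Protocol 5.11.3.4), and any ATIMP-related SAE is handled as a SUSAR (Protocol 5.11.3.4.4).
- The AE summary tables in SAP 6.1 are limited to treatment-emergent events, so months 6 to 12 fall outside them. The listings in SAP 6.1 cover AEs and SAEs without a stated time limit.

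**5. Illustration only, with assumed rates**
Take n = 32 immediate participants (the planned maximum), an assumed 12-month risk R, and a constant hazard. The 9-week risk is 1 − (1 − R)^(63/365).

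| Assumed R | Expected with event by 12 months, 32 × R | Expected within 9 weeks |
|---|---|---|
| 5% | 1.6 | 32 × 0.0088 = 0.28 |
| 10% | 3.2 | 32 × 0.0180 = 0.58 |
| 20% | 6.4 | 32 × 0.0378 = 1.21 |

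If events cluster early instead, with 90%, 75% or 50% of them in the first 9 weeks and R = 10%, the expected number missed is 3.2 × 0.10 = 0.3, 3.2 × 0.25 = 0.8 or 3.2 × 0.50 = 1.6. Under constant hazard it is 3.2 − 0.58 = 2.6. The answer depends almost entirely on timing, which the documents do not give.

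**The case against.** The strongest reply is that there is no conflict over what to compute. The two protocol sections and the SAP section that define the outcome operationally all say 9 weeks. The 12-month sentence in the summary describes a period of assessment: it continues into a further 4 years in a separate study, so it cannot sensibly be the outcome window. SAP 1.3.1 places both statements in one section. This stands. A reader might infer two rival primary outcomes; the documents support only an objective and a summary that leave out the limit.

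A reader might also infer that late events vanish from the trial's reporting. They do not: recording to trial end, SUSAR handling and the AE and SAE listings remain, and a separate follow-up study is planned to 60 months. What is missing is the composite with an interval, and the AE summaries after month 6.

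A third tempting reading is that about 83% of the safety information is lost. That figure is calendar time. Most scheduled visits fall by week 9, and Protocol 4.1.5.1 expects the risk of inflammation to be highest early after surgery.

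Finally, one window for both DLEs and the primary outcome is a defensible Phase I/II choice. Key safety results of this open-label trial were also summarised at an interim with a November 2020 cutoff, before the SAP approval date of 16 November 2021. Replacing the primary outcome after that look would be open to criticism. This argues for an added table, not a substitution.

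One limit applies to both sides: the SAP is based on protocol v12.0, while the amendment log of the protocol supplied ends at v11.0, so any alignment made in v12.0 cannot be checked.

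**Conclusion.** The point holds as a gap between the stated objective and the analysed outcome. The safety definition in Protocol 4.2.1 and 1.3 is open-ended; the headline proportion and interval stop at 9 weeks. ATIMP-related events of the same five types after that are left out of the headline, and those after month 6 are also left out of the treatment-emergent AE summaries.

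In size, the window covers 17.3% of the 12-month calendar follow-up and 34.6% of the deferred arm's 6 months after treatment, but 64% and 78% of the scheduled post-treatment visits. The number of events missed is unknown, and the illustration rests on assumed risks and timing. The documents do not support calling the 9-week outcome wrong, or concluding that late harm would go unreported. They do support reporting the composite over the whole in-study follow-up beside it.

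**What to change.** - Keep the 9-week primary safety outcome and the DLE count as specified.
- In SAP Section 6, add a co-reported table of the same five-event composite with its 95% confidence interval over full in-study follow-up after ATIMP: 12 months for escalation, paediatric and immediate participants, and 6 months for deferred participants after treatment. Label it as supplementary and added after the interim look.
- For any comparison with deferred participants before treatment, use a common 26-week window, counted from Study Day 1 as SAP 2.5 defines it for each group. Otherwise 52 weeks of exposure would be set against 26. An event cannot be attributed to the ATIMP before it is given, so the table should say how events in untreated participants are counted.
- State whether the 6-week inflammation criterion must start or be completed within each window.
- Reconcile Protocol 1.3, 4.2.1, 5.5.1 and 5.10.3.2 with SAP 1.3.1, so that the objective and the analysed outcome name the same windows.

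The cost is one more table from data already collected, plus the wording changes. For the same participants and events, the cumulative rate after treatment can only stay the same or rise relative to the 9-week figure, so the addition cannot flatter the product.

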1.4 Roles and responsibilities

Agreements that include detailed roles and responsibilities will be in place between participating sites and MeiraGTx UK II Ltd.

These membership lists are correct at the time of writing; please see terms of reference documentation in the TMF for current lists.

1.4.2 Independent Data Monitoring Committee

Name	Affiliation	Role and responsibilities

2 Trial Diagram

^{*} If randomised to the deferred treatment arm ATIMP administration will occur 6 months after screening, follow-up post administration will be for 6 months

3 Abbreviations

AAV	Adeno-Associated Virus
Ad	Adenovirus
AE	Adverse Event
AF	Autofluorescence
AO	Adaptive Optics
AR	Adverse Reaction
ATIMP	Advanced Therapy
	Investigational Medicinal
	Product
bps	Basepairs
BGL65p	hRPE65 promoter fragment
	that is less efficient than the
	NA65p promoter
BNF	British National Formulary
CAI	Codon Adaptation Index
cDNA	complementary
	Deoxyribonucleic Acid
CGIC	Clinician Global Impression of
	Change
CI	Chief Investigator
CMT	Clinical Management Team
CMV	Cytomegalovirus
CNS	Central nervous system
CRF	Case Report Form
CRO	Contract Research Organization
CTA	Clinical Trial Authorisation
CTIMP	Clinical Trial of Investigational
	Medicinal Product
DAPI	4',6-diamidino-2-phenylindole
DLE	Dose-limiting event
DNA	Deoxyribonucleic acid
DSUR	Development Safety Update
	Report
EC	European Commission
eGFP	enhanced green fluorescent
	protein
ELISA	Enzyme-linked Immunosorbent
	Assay
ELISPOT	Enzyme-linked ImmunoSpot
	Assay
EMA	European Medicines
	Agency
EOSRDs	early-onset severe retinal
	dystrophies

EQ-5D-5L	EuroQOL Quality of Life 5
	dimension 5 level
ERG	Electroretinography
ETDRS	Early Treatment Diabetic
	Retinopathy Study
EU	European Union
EUCTD	European Clinical Trials
	Directive
EudraCT	European Clinical Trials
	Database
EudraVIGILANCE	European database for
	Pharmacovigilance
FAF	Fundus Autofluorescence
FDA	(US) Food and Drug
	Administration
FWA	Federal Wide Assurance
GCP	Good Clinical Practice
GFP	Green Fluorescent Protein
GLP	Good Laboratory Practice
GMO	Genetically Modified Organism
GMP	Good Manufacturing Practice
GMSC	Genetic Modification Safety
	Committee
GTAC	Gene Therapy Advisory
	Committee
H&E	haematoxylin and eosin
hEBs	Human embryonic bodies
HEK293T	human embryonic kidney
	epithelial cell line
hRPE65	human retinal pigment
	epitheliumspecific protein 65
	(all-trans-retinyl isomerase)
HSE	Health and Safety Executive
HTA	Human Tissue Authority
H2B	histone H2B
IB	Investigator Brochure
ICF	Informed Consent Form
ICH	International Conference on
	Harmonisation
IDMC	Independent Data Monitoring
	Committee
IMP	Investigational Medicinal
	Product
IMPD	Investigational Medicinal
	Product Dossier

IND	Investigational New Drug
IRB	Institutional Review Board
ISF	Investigator Site File
ISRCTN	International Standard
ISINCTIV	Randomised Trial Number
ITRs	Inverted terminal repeats
ITT	Intention to Treat
IV (or iv)	Intravenously
IVI	Impact of Visual Impairment
1 1 1	impact or visual impairment
LCA	Leber congenital amaurosis
LCA2	
LCAZ	Retinal dystrophy associated with defects in RPE65
110	
LLQ LRFC	Local Research Ethics
LKEC	Local Research Ethics Committee
N 4 A	
MA DEC	Marketing authorisation
Main REC	Main Research Ethics
AALIDA	Committee
MHRA	Medicines and Healthcare
1401	products Regulatory Agency
MRI	Magnetic Resonance Imaging
mRNA	Messenger RNA
NA65p	Optimised hRPE65 promoter
NHS R&D	National Health Service
	Research & Development
NIH	National Institutes of Health
NIMP	Non-Investigational Medicinal
	Product
NRES	NHS National Research Ethics
	Service
NZW	New Zealand White
OBA	Office of Biotechnology
	Activities
OCT	Optical Coherence Tomography
ONL	Outer nuclear layer
ORF15	open reading frame 15
PCT	Polymerase Chain Reaction
PERG	Pattern Electroretinogram
PGIC	Patient Global Impression of Change
PGIS	Patient Global Impression of
	Severity
PHI	Protected Health Information
PI	Principal Investigator
PIS	Participant Information Sheet
0	. ar dolpane information sheet

QA	Quality Assurance		
QALY	Quality Adjusted Life Year		
QC	Quality Control		
qds	quarter die sumendus (four		
	times a day)		
QOL	Quality of Life		
QMMP	Quality Management and		
	Monitoring Plan		
qPCR	Quantitative Polymerase Chain		
	Reaction		
QP	Qualified Person for release of		
- DCD	CTIMP		
qPCR	Quantitative polymerase chain reaction		
rAAV	Recombinant adeno associated		
IAAV	virus		
rAAV2	recombinant adeno-associated		
17002	virus serotype 2		
R&D	Research and Development		
REC	Research Ethics Committee		
RG	Research grade		
RK	Rhodopsin Kinase		
RNA	Ribonucleic acid		
RPE	Retinal Pigment Epithelium		
RPE65	retinal pigment		
	epitheliumspecific protein 65		
	(all-trans-retinyl isomerase)		
RPGR	retinitis pigmentosa GTPase		
	regulator		
rt-PCR	reverse transcription		
CAE	polymerase chain reaction		
SAE	Serious Adverse Event Statistical Analysis Plan		
SAP	Serious Adverse Reaction		
SD	standard deviation		
SDV	Source Data Verification		
SOP	Standard Operating Procedure		
SmPC	Summary of Product		
3 3	Characteristics		
SSA	Site Specific Approval		
SSAR	Suspected Serious Adverse		
	Reaction		
SUSAR	Suspected Unexpected Serious		
	Adverse Reaction		
SV40	Simian virus 40		
TEI	Treatment Experience		
	Interview		

TMF	Trial Master File
ToR	Terms of Reference
tRNA	Transfer ribonucleic acid
UAR	Unexpected Adverse Reaction
XLRP	X-linked retinitis pigmentosa

USA	United States of America
vg	Viral Genomes
WT	Wild type

4 Introduction

